Official title: The effects of fractional CO2 laser on Poikiloderma of Civatte

NCT number: NCT04581330

IRB Approved date: 09-09-2020

**The University of Texas Southwestern Medical Center at Dallas
Institutional Review Board**

Protocol Template (for Investigator Initiated Studies)

Title: The effects of fractional CO₂ laser on Poikiloderma of Civatte

Principal investigator: [name].

Funding Sponsor: UTSW Dept of Dermatology

IND Number (if applicable):

Version number and date: Version 1; 7/19/2020

Introduction and Purpose: This study will assess the safety and efficacy of fractional CO₂ laser treatment for Poikiloderma of Civatte (POC). POC is a chronic vascular and pigmentary disorder typically involving the lateral and inferior neck region, as well as the chest area. Clinically, poikiloderma appears as a combination of telangiectasia, irregular pigmentation, and atrophic changes¹. Previously studied effective treatments of POC include pulsed dye lasers and IPL devices.^{2,3,4,5} Ineffective treatments include hydroquinone, electrosurgery, argon laser photocoagulation, and cryotherapy.⁶ Although PDL and IPL laser technologies are relatively safe, there have been a few reports of PDL treatment with subsequent complications, which may include ulceration developing immediately after treatment as well as scarring.^{7,8,9,10} Additionally,

¹ Arielle NB Kauvar MD, Agneta Troilius MD PhD, Chapter 39. Laser and Light Treatment of Acquired and Congenital Vascular Lesions. *Surgery of the Skin*, 2005 Pages 625-644. Available online 18 September 2013.

² Haywood RM, Monk BE. Treatment of poikiloderma of Civatte with the pulsed dye laser: a series of seven cases. *J Cutan Laser Ther*. 1999;1(1):45-48. doi:10.1080/14628839950517093

³ Clark RE, Jimenez-Acosta F. Poikiloderma of Civatte. Resolution after treatment with the pulsed dye laser. *N C Med J*. 1994;55(6):234-235.

⁴ Goldman MP, Weiss RA. Treatment of poikiloderma of Civatte on the neck with an intense pulsed light source. *Plast Reconstr Surg*. 2001 May;107(6):1376-81. PubMed PMID: 11335804.

⁵ Wheeland RG, Applebaum J. Flashlamp-pumped pulsed dye laser therapy for poikiloderma of Civatte. *J Dermatol Surg Oncol*. 1990 Jan;16(1):12-6. PubMed PMID: 2299018.

⁶ Geronemus R. Poikiloderma of Civatte. *Arch Dermatol*. 1990;126(4):547-548. doi:10.1001/archderm.1990.01670280133038

⁷ Levine VJ, Geronemus RG. Adverse effects associated with the 577- and 585-nanometer pulsed dye laser in the treatment of cutaneous vascular lesions: a study of 500 patients. *J Am Acad Dermatol*. 1995;32:613-617.

⁸ Witman PM, Wagner AM, Scherer K, et al. Complications following pulsed dye laser treatment of superficial hemangiomas. *Lasers Surg Med*. 2006;38:116-123.

⁹ Sommer S, Sheehan-Dare RA. Atrophic blanche-like scarring after pulsed dye laser treatment. *J Am Acad Dermatol*. 1999;41:100-102.

¹⁰ [name]; [name]. Linear Scarring Following Treatment With a 595-nm Pulsed Dye Laser. *Cutis*. 2014 August;94(2):83-85

PDL and IPL laser treatments require multiple sessions before seeing a clinically significant effect and do not address textural issues.¹¹ Therefore, alternative safe and effective options for management of POC are still needed. Fractional CO₂ laser has been widely used for photoaging due to its effectiveness and high safety profile.^{12,13} Clinically evident improvement can be appreciated even after only one session of treatment.¹³

One previous study showed that ablative fractional laser resurfacing was both safe and effective for the treatment of the vascular, pigmentary and textural components of POC.¹⁴ Little data exist regarding the use of fractional CO₂ laser for management of POC. This study hopes to fulfill this purpose.

2. Background

Poikiloderma of Civatte (POC) is characterized by vascular and pigmented lesions consisting of linear telangiectasias, mottled dyspigmentation and superficial atrophy in a reticular pattern found on sun-exposed areas of the face and neck, often sparing the shaded, submental area.^{15,16} Fair-skinned women in their 4th and 7th decades of life are predominantly affected.¹⁵ Most cases are benign and asymptomatic, however, some report symptoms of pruritus, burning sensation and flushing triggered by sun exposure.¹⁵ The cosmetically unappealing lesions can be distressing to affected individuals. The cause of POC is multifactorial. Chronic sun exposure,

¹¹ Hruza, George. *Lasers and Lights: Procedures in Cosmetic Dermatology Series*. Elsevier, 2018.

¹² Tierney EP, Hanke CW. Fractionated carbon dioxide laser treatment of photoaging: prospective study in 45 patients and review of the literature. *Dermatol Surg*. 2011;37(9):1279-1290. doi:10.1111/j.1524-4725.2011.02082.x

The study subjects' neck and décolletage area will be divided into two equal halves. The line of division will be from the mid mental protuberance to manubriosternal junction. One half of the neck and upper chest area will be treated with ablative fractional CO2 laser while the other half will be untreated and used as a control. If desired after the study endpoint, patients may have the other side of their neck treated at no additional charge.

Primary Outcome Measures:

Physician's Global Aesthetic Improvement Scale at 12- and 24-weeks post treatment.

Photographs will be presented to a panel of independent dermatologists. The panel will be blinded to treatment parameters and the treatment laterality at each photograph time point. Each

²⁶ Ramsdell WM. Fractional carbon dioxide laser resurfacing. *Semin Plast Surg.* 2012;26(3):125-130. doi:10.1055/s-0032-1329414

²⁷ Omi T, Numano K. The Role of the CO2 Laser and Fractional CO2 Laser in Dermatology. *Laser Ther.* 2014;23(1):49-60. doi:10.5978/islsm.14-RE-01

dermatologist will be asked to identify the baseline and post-treatment images from randomized, paired images for all subjects. Reviewers will rate improvement in POC in 10% increments on a 10-point scale (0% no improvement to 100% or complete clearance)

Secondary Outcome Measures

Subject Satisfaction Assessment at 12- and 24-weeks post treatment. Subjects will assess overall satisfaction with improvement of poikiloderma of civatte using an 5-point satisfaction and aesthetic scale.

Study subjects will be followed for 24 weeks post-laser treatment to assess incidence and severity of all procedure-related adverse events.

4. Study procedures

Patients with a clinical diagnosis of POC defined by a skin change with atrophy, hypopigmentation, hyperpigmentation, dilation of the fine blood vessels (telangiectasia) will be recruited. Ten patients will be consented. Before the initial visit, all patients will complete a one-month preoperative daily use of SPF 50+ sunscreen. The sun protection is to reduce further sun damage and protect skin from increased photosensitivity that may occur after laser resurfacing. At the initial visit, high resolution photographs of the affected area on the neck and décolletage area will be taken. All patients will fill out a form with demographic information. Patients will be instructed to come to their appointment with clean skin and without any lotions or moisturizers on the neck or décolletage area. Laser-specific eyewear will be provided to practitioners, patients, and all other people in the treatment room. A blue skin marking pen will be used to draw a line from mid mental protuberance to manubriosternal junction to divide tested area into two equal halves. Compounded benzocaine, lidocaine, and tetracaine (BLT) cream in a 20:8:4% concentration will be applied to the treatment area for 40 minutes prior to the procedure. Before

the treatment, topical anesthesia will be thoroughly washed off with chlorhexidine gluconate and distilled water. One pass with a 1-mm spot density and a 60micron depth will be performed followed by a 1mm spot density and a 200-micron depth will be used. The other half of the testing area will be left intact and used as the control for easy comparison. The side that undergoes treatment will be selected randomly. Forced cold air (Zimmer cooler) will also be used in conjunction with the laser device for better patient comfort.

Cold compresses with refrigerated distilled water can be used to reduce swelling and to soothe the skin with frequent reapplication of white petrolatum to keep the skin coated for days 1-5 post-procedure with strict sun avoidance for the first week post-procedure. Daily use of broad-spectrum sunscreen with SPF50+ will be required after the first week.

Given the current pandemic, limited in-person follow-ups will be scheduled (once at baseline before treatment, then at 12 and 24-weeks post-treatment. Participants will communicate immediate post-treatment issues or concerns along with selfies through MyChart on day 2, 3, 7, 10, 14 to track progress and to identify any post procedural complications in a timely fashion. There will also be no costs to the patients for the laser procedures as funding will be supplied by the UT Southwestern Dermatology department via an educational grant. Patients desiring treatment of the control side after the study end-point (24 weeks) will be provided at no cost for the participants.

5. Sub-Study Procedures: N/A

6. Criteria for Inclusion of Subjects

- Male and female subjects, English and non-English speakers, and subjects more than 18 years old
- Clinical diagnosis of poikiloderma of Civatte affecting the neck and chest

- Agree to not undergo any other procedures on the neck and chest area during the study
- Agree to refrain from tanning for 6 months post-procedure
- Willing and able to read, understand, and sign the consent form
- Willing and able to adhere to the treatment and follow-up schedule as well as post-treatment care

7. Criteria for Exclusion of Subjects

- Patients under 18 years old
- Active skin infection, dermatitis, or a rash on the treatment area
- Pregnant or lactating patients
- Patients on immunosuppressive medications
- Any laser procedures or chemical peel procedures on the neck or chest area within the past 6 months
- Patients with multiple comorbidities such as diabetes mellitus, cardiovascular diseases, neurologic disorders, internal malignancies
- Personal history or family history of forming keloids or hypertrophic scars, or abnormal wound healing
- Patients with known bleeding disorders or taking more than one anticoagulation medications
- Undergoing any surgery in the treatment area within the past 12 months
- History of radiation to the head, neck, and chest area
- Systemic use of isotretinoin within 6 months
- Any use of gold therapy
- Current smoker or history of smoking within 12 months of study

- Any physical or mental condition in which the investigators deem unsafe for the subject to participate in the study.
- History of recurrent herpes simplex on the neck or chest.

8. Sources of Research Material

Sources of materials used during this study will include data collected from patient surveys, data collected from blinded dermatologists' assessment, and pictures taken of the participants. These materials and data will be obtained at each patient visit. Given the current pandemic, only limited in-person follow-ups will be scheduled (once at baseline before treatment, then at 12 weeks, 24 weeks). Participants will communicate immediate post-treatment issues or concerns along with selfies through MyChart on day 2, 3, 7, 10, 14 to track progress and to identify any post-procedural complications in a timely fashion. Materials and data gathered will be obtained specifically for research purposes, and no existing records or specimens will be used.

9. Recruitment Methods and Consenting Process

Subjects will be identified from patients presenting to the dermatology department at UT Southwestern. When a patient with POC is identified, they will be offered inclusion in the study. Informed consent will be obtained. Both English and non-English speaking patients will be included. If the patient is non-English speaking, a certified translator will be used to obtain consent. Each patient will be informed that he or she has the right to withdraw consent and terminate participation in the study at any point if he or she so desires. No vulnerable populations (cognitively impaired, institutionalized, children) will be included in the study to minimize the risk of undue influence or coercion.

10. Potential Risks:

- Ocular – severe ocular complications such as corneal ulceration and cataract could happen with any laser devices. Therefore, CO2 laser specific eyewear will be provided to everyone in the treatment room. Ocular complication for this study should be low since we are mainly targeting the neck and upper chest area instead of the facial area.
- Pain – Topical anesthesia, and a forced-air cooling device will be used to help patients tolerate the procedure. Prolonged severe pain postoperatively may indicate other complications such as infection and patient should contact the investigators and will be examined in-person to determine the cause.
- Infection – patients will be counseled on signs of infection such as increased erythema, purulence, oozing and crusting. Patients will submit electronic selfies of the treatment area electronically to investigators on day 2, 3, 5, 7 and 10. Investigators will contact patients if any signs of infection are identified. For patients with skin infection within the past 6 months, topical mupirocin ointment TID applied to the nares will be prescribed to prevent staph colonization.
- Post-inflammatory hyperpigmentation: This usually happen less frequently in lighter skin types which are the groups most commonly affected by POC. However, should this occur, hydroquinone and topical retinoids can be prescribed for the patient at the study end-point to alleviate the dyschromia.
- Prolonged erythema: if erythema lasts more than 3 weeks postoperatively, a mid-potency topical steroid will be prescribed to the patient.
- Scarring: patients with personal and family history of keloid disease and hypertrophic scar formation will be excluded from the study. If hypertrophic or keloidal scars happen, intralesional steroids will be used to flatten the scars.

11. Subject Safety and Data Monitoring

All treatments will be completed at the Dermatology clinics at UT Southwestern where there are adequate resources for medical intervention in case of an adverse event such as increased bleeding, pain, or infection. The risk of severe bleeding is minimal and does not warrant the need for spare blood products or type and screening.

12. Procedures to Maintain Confidentiality

The study materials will not be disclosed to any outside persons or entities. Patient surveys collected will be stored securely in files in the dermatology offices and will not be removed from campus.

13. Potential Benefits

- Improved overall dyschromia and telangiectasia of the chest and neck area
- Overall increased patient satisfaction and quality of life
- Provide patients safe and effective alternative for treatment of discoloration and atrophy of neck and chest area which hopefully can be generalized to similar patient populations.

14. Biostatistics

Descriptive statistics will be used to summarize patient demographics. Count (%) will be used for categorical variables; and mean, standard deviation (SD), and range (min/max) will be used to summarize continuous variables with approximately normal distributions. Skewed continuous variables will be summarized by median and interquartile range (IQR). Outcome data will be collected on patient satisfaction assessment scores and physician's global aesthetic improvement scores, as well as assessment of adverse events. The Wilcoxon signed rank test will be used to compare the magnitude of change between the baseline scores and post-intervention scores. The Wilcoxon signed rank test will also be used to compare the magnitude of change of the treated

area and the control area. A p-score of <0.05 will be considered statistically significant. The target sample size is 10 people.

Outcome Measurement:

Global Aesthetic Improvement Scale`

| | Degree | Description |
|---|-------------------------|--|
| 1 | Exceptional improvement | Excellent corrective result |
| 2 | Very improved patient | Marked improvement of the appearance, but not completely optimal |
| 3 | Improved patient | Improvement of the appearance, better compared with the initial condition, but a touch-up is advised |
| 4 | Unaltered patient | The appearance substantially remains the same compared with the original condition |
| 5 | Worsened patient | The appearance has worsened compared with the original condition |

Patient Satisfaction Assessment

| | | | | |
|--|--|--|---|--|
|  |  |  |  |  |
|  |  |  |  |  |
| Very Unsatisfied | Unsatisfied | Neutral | Satisfied | Very Satisfied |

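### The named primary (five-grade GAIS) and the only rating procedure described under it (a 0-100% panel score with no value for worsening) are not reconciled

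*Combined protocol and SAP*

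**What the plan says.** Section 3, Primary Outcome Measures, names the Physician's "Global Aesthetic Improvement Scale at 12- and 24-weeks post treatment". The procedure that follows is for a panel of independent dermatologists, blinded to laterality and treatment parameters. Each "dermatologist will be asked to identify the baseline and post-treatment images from randomized, paired images for all subjects". Then: "Reviewers will rate improvement in POC in 10% increments on a 10-point scale (0% no improvement to 100% or complete clearance". GAIS is not mentioned in that procedure.

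Section 14, Biostatistics, says outcome data will include patient satisfaction scores and the physician's "global aesthetic improvement scores, as well as assessment of adverse events". Two Wilcoxon analyses follow. For the between-side one, "The Wilcoxon signed rank test will also be used to compare the magnitude of change of the treated" area and the control area; no scale is named. The Outcome Measurement table then prints GAIS as five grades, with 1 the best result and 5 defined as "The appearance has worsened compared with the original condition". The percent rating does not appear in Section 14.

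Under secondary outcomes, Section 3 also plans 24 weeks of follow-up "to assess incidence and severity of all procedure-related adverse events".

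**The concern.** The primary endpoint is described in two ways that do not meet. The scale that has grades and is listed for analysis has no stated rater, material or blinding. The scale that has a blinded rating procedure is not listed for analysis. A panel that follows Section 3 to the letter will hand over percentages, and Section 14 has no stated use for them.

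The difference matters because the percent scale stops at no improvement. A treated side that worsens can score no lower than one that has not changed. If that score were tested, worsening might not count against the laser in the efficacy comparison. Adverse-event follow-up would record the harm separately but would not alter that test. With 10 patients, a few such sides can decide significance. If the scale is settled only after the ratings are seen, the result is open to challenge.

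**Working it through.** **Plan's own figure.** The target is 10 people, with no effect size, SD or power behind it, so there is nothing to reproduce.

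**Scales side by side.**

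| | Percent score (Section 3) | GAIS (Section 14) |
|---|---|---|
| Values | (100 − 0)/10 + 1 = 11, though called 10-point | 5 |
| Better direction | higher | lower |
| Worsening | no value | grade 5 |
| Blinded panel procedure | yes | not stated |
| Listed as outcome data for analysis | no | yes |

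No cut-points convert one to the other, and a score with a floor at 0% cannot yield grade 5.

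**Effect on the treated-versus-control test.** The inputs are assumptions, not document figures: 10 pairs, unchanged controls, k treated sides worse by one grade, and the rest improved by one or two grades. On GAIS the images are correctly ordered. On percent, worsened sides score 0%. The test is the exact two-sided signed-rank test (the plan does not state sidedness), with zeros dropped and mid-ranks for ties.

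For k = 2:
- GAIS, all eight improvers one grade: ten tied ranks, p = 2 × (1 + 10 + 45)/1024 = 112/1024 = 0.109.
- GAIS, four improvers one grade and four two grades: mid-ranks 3.5 (six) and 8.5 (four), W− = 7, p = 2 × (1 + 6 + 15)/1024 = 0.043.
- GAIS, all eight two grades: mid-ranks 1.5 (two) and 6.5 (eight), W− = 3, p = 2 × 4/1024 = 0.008.
- Percent: two zeros drop out, p = 2/2^8 = 0.008. Keeping zeros in the ranking (Pratt) gives the same.

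| k worsened | GAIS p, all one grade to all two grades | Percent p = 2/2^(10−k) | Verdicts at 0.05 differ |
|---|---|---|---|
| 0 | 0.002 | 0.002 | never |
| 1 | 0.021 (22/1024) to 0.004 | 0.004 | never |
| 2 | 0.109 to 0.008 | 0.008 | if at most 3 of 8 improvers move two grades |
| 3 | 0.344 to 0.016 | 0.016 | if at most 5 of 7 do |
| 4 | 0.754 to 0.090 | 0.031 | always |

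**Image order.** Take k = 2 again, with one-grade improvers on GAIS and 20% improvers on percent.

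| Handling of the two worsened pairs | GAIS p | Percent p |
|---|---|---|
| Recorded as worsening (percent: −20%) | 0.109 | 0.109 |
| Scored 0% | n/a | 0.008 |
| Excluded | 2/2^8 = 0.008 | 0.008 |
| Misread as improvement | 2/2^10 = 0.002 | 0.002 |

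The contrast comes from the floor and from how misidentified pairs are handled. GAIS has no advantage if such pairs are misread or excluded.

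**Coarseness, with no worsening.** Suppose s sides improve by 10% and are graded unaltered on GAIS, and the rest improve by one grade. Then GAIS p = 2/2^(10−s): 0.031 at s = 4, 0.063 at s = 5, 0.25 at s = 7. Percent p is 2/1024 = 0.002 throughout. If 10% is graded as improved, both give 0.002. The k = 0 row above assumes that every treated side changes grade, so the two results do not conflict.

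**Power, illustrative.** With 3,000 simulated trials (treated mean 20, SD 20; control mean 0, SD 10), GAIS gives 33-53% over five assumed cut-point sets and the floored percent score 72%. In a further illustrative run, a percent score allowed below zero gave about 66%, against 73% floored. A separate simulation (SD 15 or 25, true differences of 10 to 40 points) gave opposite significance decisions on the two scales in about 5-27% of trials.

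**The case against.** The best reply is that GAIS is plainly what will be analysed: it is the named primary, Section 14 defines its grades and lists its scores directly before the tests, and the percent score is absent there. That is the more natural reading. A reader might go further and infer that GAIS is left undefined, or that the primary test will run on the percent score and conceal harm. The documents support neither. But under the natural reading, the primary has no described rater or blinding, because the blinded procedure yields something else. The GAIS grades are also worded for a whole patient, and no text says each side receives one.

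A second reply is that the percent score, placed under the primary heading, is how GAIS is put into practice. That rests on placement alone, and the percent score cannot produce the worsened grade.

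A third reply is that the worsening example favours GAIS by assuming its images are correctly ordered while the percent score loses the worsened sides. This stands. Raters must first pick the baseline image, and the plan does not say how a wrong pick is scored. A rater who takes the better image as post-treatment would grade a worsened side as improved on either scale.

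It also stands that no rate of worsening is given. Verdicts in the grid differ only with two to four worsened sides of ten, and Section 1 cites a study reporting ablative fractional resurfacing as safe and effective in this condition. Against that, Section 10 lists hyperpigmentation, prolonged erythema and scarring as risks, so worsening is foreseeable.

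**Conclusion.** The point holds and should be fixed. Sections 3 and 14 conflict on the primary endpoint: the described panel procedure produces no GAIS grade and has no place for worsening, while the analysis section lists GAIS. Confidence in that textual finding is high.

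The size of the consequence is conditional. On assumed data with correctly ordered images, the same ten patients can give p = 0.109 or 0.008 depending on scale. When every treated side changes grade, verdicts do not differ with no or one worsened side. The contrast also disappears if worsened pairs are misread or excluded on GAIS. These figures show that the choice can decide the result at n = 10; they do not show that it will.

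A reader might also infer that GAIS must be chosen. That does not follow. What is needed is one scale that records worsening, and a percent score extended below zero would also serve.

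**What to change.** Before any photograph is rated, reconcile Sections 3 and 14:

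- Name one primary scale that can record worsening: either the five-grade GAIS already named, or the percent score extended below 0%. Make the other rating secondary, and describe the 0-100% scale as having 11 values.
- State that the blinded panel scores the primary scale separately for the treated and control sides, state which direction is better, and state that the treated-versus-control Wilcoxon test uses it.
- Whichever scale is primary, have each panel member record which image they take as baseline and which as post-treatment. Attach the true order at analysis, so that a misidentified pair counts as worsening and is neither dropped nor counted as improvement.

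The cost is wording and a revised rating form, with no extra patients, visits or raters. If both ratings are kept, each panel member gives two scores per side. The real trade-off is power: GAIS is coarser and probably less powerful, while a signed percent scale keeps most of the percent score's power under the assumed inputs above. The sponsor should make that choice openly and before the ratings exist.

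### No rule covers an image pair that the rater puts in the wrong time order; read literally it scores as improvement, diluting a modest benefit and letting worsening look like benefit

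*Combined protocol and SAP*

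**What the plan says.** Section 3 (Primary Outcome Measures) names the primary outcome as "Physician's Global Aesthetic Improvement Scale at 12- and 24-weeks post treatment". It then describes a panel reading of photographs: "The panel will be blinded to treatment parameters and the treatment laterality at each photograph time point". Each "dermatologist will be asked to identify the baseline and post-treatment images from randomized, paired images for all subjects". The scale follows: "Reviewers will rate improvement in POC in 10% increments on a 10-point scale (0% no improvement to 100% or complete clearance". Its lowest value is no improvement, so worsening cannot be entered.

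Section 14 (Biostatistics) lists satisfaction scores, physician GAIS scores and adverse events as the outcome data. For the split-neck comparison, "The Wilcoxon signed rank test will also be used to compare the magnitude of change of the treated" and control areas, and "A p-score of <0.05 will be considered statistically significant". It does not mention the order answers or the percentage rating. It prints a five-grade GAIS whose grade 5 reads "The appearance has worsened compared with the original condition". Neither section says how the GAIS and the percentage rating are related.

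**The concern.** A rater who does not know the true order can only judge change from the image he or she calls baseline to the image he or she calls post-treatment. If that call is wrong, a high rating means that the skin looked better before treatment. Nothing in the plan decodes the order and corrects the direction before the Wilcoxon test.

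Two consequences follow if the scores are used as recorded. On an unchanged half, noise in the rater's perception always registers as zero or positive improvement, so the control mean rises and a real contrast shrinks. On a half that has become worse, the rater tends to call the worse image baseline, so worsening is recorded as improvement. Both affect the direction or size of the main efficacy comparison in a trial of 10 people.

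Adding a worse category to the percentage scale would not be enough. Its direction would still be relative to the order the rater guessed.

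**Working it through.** **Nothing to reproduce.** Section 14 gives a target of 10 people with no effect size, SD or power, so no plan figure can be checked. The calculation below shows the size of the effect under stated assumptions.

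**Inputs from the documents:** 10 subjects, within-subject comparison of halves, steps of 10 points, signed-rank test, threshold 0.05 (taken as two-sided; the plan does not say).

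**Assumptions:** one rating per half; each half shown as its own pair; halves independent; perceived change X ~ Normal(μ, s), with μ = 0 on the control half and s = 10, 15 or 20 points.

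**Scoring compared**
- Signed: X, with direction set by the true order.
- Unsigned (the literal reading): |X|, since a pair with negative perceived change is put in the wrong order and scored as positive.

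**Formulas**
- P(wrong order) = Φ(−μ/s). This is 50% on the control half.
- E|X| = s·√(2/π)·exp(−μ²/2s²) + μ·[1 − 2Φ(−μ/s)].

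**Worked case, s = 15, μ = +20**
- Control: 15 × 0.798 = 12.0.
- Treated: 12.0 × exp(−400/450) + 20 × (1 − 2 × 0.091) = 4.9 + 16.4 = 21.3.
- Unsigned contrast: 21.3 − 12.0 = 9.3, against a true 20.

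**Results.** Means are analytic, before rounding. Power is from simulated trials of 10 subjects with scores rounded to 10 points and an exact signed-rank test. With 4,000 trials the simulation error is at most √(0.5 × 0.5/4000), or about 0.8 percentage points.

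| s | Wrong order, treated half at +20 | Mean unsigned score, unchanged control | Unsigned contrast for true +20 | Power signed | Power unsigned | True −20 shown as significant benefit |
|---|---|---|---|---|---|---|
| 10 | 2% | 8.0 | +12.2 | 95% | 72% | 71% |
| 15 | 9% | 12.0 | +9.3 | 67% | 27% | 28% |
| 20 | 16% | 16.0 | +7.4 | 47% | 14% | 13% |

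The last two columns agree within simulation error, as they must: |X| has the same distribution for μ = +20 and μ = −20. Unsigned scores cannot tell a benefit from a harm of equal size.

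**Larger effect.** At +40 the power loss is small for s = 10 to 15 (98% against over 99% at s = 15). At s = 20 it is 79% against 96%.

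**No change on either half.** The expected contrast is 0 under both scorings. In a run using the normal approximation to the signed-rank test, unsigned scores rejected in 3.5% (s = 10) and 4.9% (s = 20) of trials, so the treated-control type I error is not inflated.

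**The case against.** **The text is silent, not explicit.** The order might be revealed before rating, a wrong-order pair might score 0, or it might be re-signed. This stands as a limit on what can be claimed: a reader might infer that the plan counts wrong-order pairs as improvement and discards the order answers, but the documents only leave both unspecified. If the order is known and worsening is scored 0, a true +20 becomes 16.1, 14.7 or 13.7 (s = 10, 15, 20) and a true −20 becomes −3.9, −5.3 or −6.3. Harm is then understated, not reversed. Silence is still a fault, because a scoring rule chosen after the ratings are seen could change the result.

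**The named primary outcome, the GAIS, has a worsened grade.** If it is graded with the true order known, this mechanism does not touch it. If it is graded from the same order-masked pairs, worsened is again relative to a guess. The plan does not say which.

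**Harm would be seen elsewhere.** It is tempting to conclude that the trial could hide harm. The documents do not support that: Section 3 collects procedure-related adverse events for 24 weeks and Section 4 adds patient photographs. A visible scar might also identify the post-treatment image. The problem concerns the efficacy rating.

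**The size rests on assumed noise and one rater.** Correct. Section 3 specifies a panel. Averaging three independent raters (an assumption) at s = 15 raises unsigned power at +20 from about 27% to about 75%. By the symmetry shown in the working, it equally raises the chance that a −20 harm is declared a benefit, so averaging does not cure the sign.

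**Half the control scores are not wrong-signed.** The 50% is the rate of wrong order calls. With rounding to 10 points and s = 15, about 26% of control scores are 0 and about 37%, Φ(−5/15), carry the wrong sign.

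**Conclusion.** The point holds as a conditional one. The plan has order-masked raters score improvement on a scale with no negative side, gives no rule for a wrongly ordered pair and assigns the order answers no use. Followed literally, it dilutes a modest true benefit and can turn worsening into apparent benefit.

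The magnitudes are those tabulated above. They rest on 10 subjects, one rating per half, separate and independent pairs, and noise SDs that the documents do not give. Averaging several raters would reduce the power loss.

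Two stronger conclusions should not be drawn: that the treated-control test gives too many false positives when neither half changes, or that the plan actually prescribes counting harm as benefit. The case for acting is that the primary rating's direction is left undefined and defining it is nearly free.

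**What to change.** In Sections 3 and 14, before any images are read, state that:

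1. Raters choose the order of each pair and then score the size of the change.
2. After all scores are locked, the true order key is applied. A wrongly ordered pair enters the analysis as worsening, with a negative sign, before any Wilcoxon test.
3. The result is treated as an ordinal signed score. A percentage change is not exactly reversible: if the second image has half the severity of the first (50% better), the first is 100% worse than the second.
4. The GAIS follows the same true-order convention, and its relation to the 0–100% rating is stated.
5. The percentage of correct order calls is reported for treated and control halves, descriptively only.

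Do not make 50% on the control half a required masking check. Sun protection and tanning avoidance (Sections 4 and 6) may change that half, and a photograph showing both halves could reveal the order.

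The cost is a few sentences and one recoding step, with no new data, visits or raters. Mean scores may look slightly less favourable.
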